12. MEDICATIONS

Medications will be coded using WHO-DD version specified in the data management plan and will be presented by Anatomical Therapeutic Chemical (ATC) (the 1st level of the ATC code) and PT for the RND analysis set. Medications may be assigned to multiple treatment groups based on their occurrence date, due to the cross-over design of the study. Certain medications (or a special grouping of medications) will be classified in a list during the study and signed-off prior to lock by a medical advisor. As this list, may change prior to sign-off they will not be defined in this section of the SAP. Potential medications include, but are not limited to, inhaled corticosteroids (ICS), LAMAs (long-acting muscarinic antagonists), LABAs (long-acting beta2-agonists) etc.

See Appendix 2 for handling of partial dates for medications, in the case where it is not possible to define a medication as prior, concomitant, or post treatment, the medication will be classified by the worst case; i.e.

Document: Z:\RPL554\UYA25849\Biostatistics\Documentation\SAP\Verona RPL554-CO-204 SAP v1.0

Author: [name] Version Number: 1.0

Version Date: [18OCT2018]

Template No.: CS_TP_BS016 Revision 5 Reference: CS_WI_BS005

Effective Date: 01Apr2018

Page 24 of 50

concomitant.

- 'Prior' medications are medications which started and stopped in the 3 months prior to the first dose of study medication and are recorded at Screening.
- 'Concomitant' medications are medications which:
 - Started 3 months prior to first dose of each study medication and on or after the first dose of each study medication.
 - o AND ended on or after the date of first dose of study medication or were ongoing at the end of the study.
 - A patient can report more than 1 concomitant medication with the same PT, but concomitant medication will be counted only once. Similarly, if a patient reported more than 1 concomitant within the same primary ATC Level 1, the patient will be counted only once. However, a medication can be counted once per treatment period, if it occurs in multiple treatment periods.

Prior and concomitant medications will be presented in a listing only, by treatment group.

- Rescue medications will be recorded on the Rescue Medication page of the eCRF. These are short acting bronchodilators and will be sourced by the study center and dispensed at the Screening visit. Rescue medication used during each treatment period must be separately documented on the eCRF (medication, dose, route, date and time of each administration). Protocol procedures must continue even if rescue medication has been taken. Salbutamol/albuterol is to be used for primary rescue use. Salbutamol/albuterol and ipratropium (or Combivent®) must be withheld for at least 8 hours prior to spirometry (per below), and this is to be confirmed in the eCRF at the start of each treatment period. If this withhold is not met, the patient should be rescheduled for a repeat visit within permitted windows. Short acting bronchodilators should be withheld as follows:
 - o 8 hours prior to pre-reversibility spirometry for Screening
 - o 8 hours prior to pre-dose spirometry for Day 1, Day 2 and Day 3
 - o Post dose:
 - Day 1 until after +12 hours spirometry.
 - Day 2 until after + 12 hours spirometry.
 - Day 3 until after + 24 hours spirometry (Day 4 morning).

Rescue medications used (during the treatment periods) will be summarized by treatment group and the type of

Document: Z:\RPL554\UYA25849\Biostatistics\Documentation\SAP\Verona RPL554-CO-204 SAP v1.0

Author: [name] Version Number: 1.0

Version Date: [18OCT2018]

Template No.: CS_TP_BS016 Revision 5 Reference: CS_WI_BS005

Effective Date: 01Apr2018

Page 25 of 50

rescue medications, presented in a table. Time to first use of rescue medication will also be estimated for each treatment group, where start time is considered the time of first dose administration in treatment period 1 and end time the time when first rescue medication was used or the time of last spirometry (24 h after evening dose 3) performed in the period. Kaplan-Meier estimates, if calculable, for median time to first overall fall with 95% confidence interval, minimum, 25th and 75th percentiles and maximum will be presented for each treatment group. An accompanying Kaplan-Meier figure will also be presented, including all available rescue medications recoded from patients. Patients not experiencing a use of rescue medications will be censored at the time of last spirometry within treatment period or premature discontinuation. If rescue medication usage is deemed to be low (number of patients using rescue medications < 10%), as expected, the Kaplan-Meier estimates and accompanying figure will not be presented. Rescue medications will also be presented in a listing.

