9.4.5 Efficacy/Pharmacodynamics

FEV₁ and FVC will be summarized as actual and change from baseline using descriptive statistics over time.

The peak effect on FEV_1 during these time intervals will be computed as the maximum value in the 4 hours after dosing. The average effect will be calculated as the AUC divided by the length of the time interval of interest. For analysis, the peak, average and trough FEV_1 will be divided by the pre-dose Day 1 baseline value.

Computed pharmacodynamic parameters for FEV_1 will be compared between the three study treatments using analysis of covariance (ANCOVA) models with fixed factors for treatment, period and patient, and using the pre-dose Day 1 baseline value as a covariate. FEV_1 will be analyzed using multiplicative models, which means that data (dependent and baseline) are logged prior to analysis and the result then transformed back to the linear scale giving treatment differences as ratios of geometric means.

Primarily the combination RPL554+tiotropium/olodaterol will be compared to tiotropium/olodaterol alone for each of the two doses of RPL554. Results of the comparisons will be expressed as the mean geometric ratio with 95% confidence intervals and associated, 2-sided, p-value.

Onset of action will be summarized by treatment and a Kaplan-Meier plot illustrating time to onset constructed.

Outcomes from the whole body plethysmography at 1.25 hours post-dose on Day 1 and 1.25, 8.25 and 12.25 hours post-dose on Day 3 will be compared in the same way as FEV₁ using multiplicative ANOVA models. The baseline of the visit (pre-first dose in a treatment period) will be used as covariate in these models.

The use of rescue medication during the study visits will be summarized by treatment, and, if appropriate, a Kaplan-Meier plot illustrating time to first use of rescue constructed.

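### SAP 12 starts time to first rescue at the Period 1 first dose but ends it within the period; SAP 13 and 13.1 misstate total washout and take the last-dose date from the Disposition page (descriptive outputs only)

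*SAP*

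**What the plan says.** **Rescue.** SAP 12 estimates time to first rescue separately for each treatment group, "where start time is considered the time of first dose administration in treatment period 1". The end is the first rescue use or "the time of last spirometry (24 h after evening dose 3) performed in the period". Patients without rescue "will be censored at the time of last spirometry within treatment period or premature discontinuation". The figure is to be drawn "including all available rescue medications recoded from patients", and the summary statistic is the "median time to first overall fall with 95% confidence interval". The same section says "Rescue medication used during each treatment period must be separately documented on the eCRF". Under the suppression rule, if use is low ("number of patients using rescue medications < 10%), as expected, the Kaplan-Meier estimates and accompanying figure will not be presented"). Protocol 9.4.5 limits the rescue summary to the study visits and plans, "if appropriate, a Kaplan-Meier plot illustrating time to first use of rescue constructed".

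**Exposure.** SAP 13 takes the first-medication date from the Drug Exposure page for Period 1. It takes the last-medication date from the completion or discontinuation date on the Disposition page, and says washouts (7 to 14 days) do not count as exposure. SAP 13.1 computes duration as last administration date minus first administration date, minus washout days between periods, plus 1. It puts those washout days at 21 to 42.

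**The concern.** In a three-period crossover, a clock that starts in Period 1 and stops within a later period counts earlier treatments and washouts as time on the later treatment. If that rule is programmed as written and the output is shown, the curves and any median cannot be read as time to rescue on a treatment.

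Two labels in the same paragraph are also wrong. The last spirometry is placed 24 h after the third evening dose, and the event is called a fall, which is not an event in this study.

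For exposure, the stated washout range fits three washouts, but three periods have two. The formula asks for a last administration date, while the stated source is a date not defined as a dosing date. How a washout day is counted is not defined either: it could be a dose-free day, or a day counted from the last dose as in Protocol 3.1. What is at stake is the accuracy of two descriptive outputs.

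**Working it through.** **Inputs.** Three periods of 3 dosing days, separated by washouts of 7 to 14 days (SAP 3.1), counted from the last Day 3 dose (Protocol 3.1). Planned treatment up to 9 days and participation up to 61 days (Protocol 3.3). Last spirometry 24 h after the Day 3 morning dose (Protocol 6.3.3.3). About 70 patients, six sequences in equal ratio (SAP 3.1).

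**Calendar.**
- 7-day washouts: dosing on study days 1-3, 10-12 and 19-21.
- 14-day washouts: dosing on study days 1-3, 17-19 and 33-35.

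**Rescue, literal start applied to all periods.**
- Period 2 offset: 10 − 1 = 9 to 17 − 1 = 16 days (216 to 384 h).
- Period 3 offset: 19 − 1 = 18 to 33 − 1 = 32 days (432 to 768 h).
- True window: 48 h to the Day 3 morning dose + 24 h = 72 h.
- Take 69 records per treatment, 23 from each period, and assume a true 72 h rate of 10%. By 72 h only Period 1 records can have events, but all 69 are at risk: 0.10 × 23 / 69 = 3.3%.
- Later events fall on smaller risk sets. Ignoring the spread of start days, the curve would end near 1 − (1 − 2.3/69)(1 − 2.3/46)(1 − 2.3/23) = 1 − 0.967 × 0.95 × 0.90 = 17%. The spread of start days shrinks the late risk sets further. In a simulation (constant hazard, washouts uniform on 7 to 14 days, 1,500 runs) the curve ended at about 30% on average. A per-period start gave 10.0%.

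**Rescue, Period 1 records only.** There is no offset, but only 70/3 ≈ 23 patients per treatment remain. At 10% the standard error is √(0.1 × 0.9/23) = 6.3 percentage points, against √(0.1 × 0.9/69) = 3.6 with all periods. This reading also conflicts with using all available rescue records.

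**Spirometry label.** The Day 3 evening dose is at 60 h, so 24 h later is 84 h. The schedule's last spirometry is at 72 h, 12 h after that dose (Protocol Table 4, footnote a). SAP 12's own withholding list also places the 24 h spirometry on the morning of Day 4.

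**Washout range.** The SAP's figure is reproduced by 3 × (7 to 14) = 21 to 42. Two washouts give 2 × (7 to 14) = 14 to 28. Cross-check: 14 screening + 9 treatment + 28 washout + 10 follow-up = 61, the protocol's maximum; with 42 the sum is 75.

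**Exposure of a completer** (last − first − washout + 1). For 7-day washouts, the dose-free days are 6 + 6 = 12 and the days from last dose are 14.

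| Last date used | Dose-free count | From-last-dose count |
|---|---|---|
| True last dose (day 21) | 21 − 1 − 12 + 1 = 9 | 21 − 1 − 14 + 1 = 7 |
| Day 4 of Period 3 (day 22) | 22 − 1 − 12 + 1 = 10 | 22 − 1 − 14 + 1 = 8 |

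For 14-day washouts (dose-free 26, from last dose 28; last dose on day 35, Day 4 on day 36) the results are the same: 9 and 7, then 10 and 8.

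**The case against.** **Intent is recoverable.** The end and censoring rules are per period, and SAP 6.2 sets baselines per period. A programmer would probably use a per-period clock. That lowers the risk, but the start rule says otherwise and should not be left to interpretation.

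**The rescue output may never appear.** The SAP expects use below 10%. The denominator is not stated; if it is the 70 patients over the whole study, the threshold is 7 patients. A 10% rate in each period would imply 1 − 0.9³ = 27% of patients over the study, assuming independence, so the illustration lies well above the use the SAP expects. The median is planned only if calculable, and in the simulation the literal curve reached 50% in only about 12% of runs. All of this stands and limits the consequence.

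**The washout range may be inert.** If each patient's actual washout days are subtracted, the 21 to 42 days has no numerical effect. This stands.

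**The Disposition date is not known.** The eCRF page is not shown. SAP 5.5 describes completion as first and last dose plus 1 day, and SAP 9 assigns discontinuations by last treatment day plus 1. Both point to Day 4 without stating it. The dose-free count also fits SAP 13 better, since it removes only non-dosing time. On those two readings the error is one day.

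**Stronger readings a reader might infer.** One is that every completer's exposure must differ from 9. The documents do not support that: if the page holds the true last-dose date, the dose-free count gives exactly 9. Another is that the last date is the end-of-study visit, which would give 14 to 20 days (12 to 18 counted from last dose). Nothing in the documents says so. A third is that the literal rescue curve simply understates use. It does so at 72 h, but it overstates use by its end.

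**Conclusion.** Wrong as written, minor. The rescue start rule contradicts its own end and censoring rules. Followed literally over all periods, it gives a curve with no usable meaning: about 3.3% at 72 h and about 30% at its end, for an assumed true 10%. The end figure rests on the simulation's constant hazard and uniform washouts; the 72 h figure rests only on equal numbers per period. Because sequences are balanced, no treatment is favoured in expectation, so this is not evidence of a biased comparison.

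The washout range is certainly wrong for three periods (14 to 28, not 21 to 42), probably without numerical effect. The last-dose source gives 10 days (8 counted from last dose) instead of 9 if the Disposition date is Day 4, which is an assumption. Unlike the rescue curve, the exposure summary has no suppression rule. Both outputs are descriptive; the primary analysis, power and hypothesis tests are unaffected.

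**What to change.** **SAP 12.** Start the clock at the first dose of study medication in the same treatment period. End it at the first rescue use in that period, or censor at that period's last spirometry (24 h after the Day 3 morning dose) or at premature discontinuation. Name the event first use of rescue medication.

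**SAP 13 and 13.1.** Compute exposure days as last minus first dosing date plus 1 within each period, summed over periods, using dosing dates from the Drug Exposure page. Delete the 21 to 42 day range. For completers this gives 3 × (3 − 1 + 1) = 9, and it needs no convention for counting washout days. The display by sequence can stay.

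**Cost.** SAP wording and programming only. Dose dates and times (Protocol 5.11) and rescue dates and times in each period (Protocol 5.10) are already recorded in the eCRF.

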13. STUDY MEDICATION EXPOSURE

Exposure to study medication in days will be presented by treatment sequence for the RND analysis set. The date of first study medication administration (tiotropium/olodaterol dosing) will be taken from the Drug Exposure eCRF page for treatment period 1. The date of last study medication will be taken from the Disposition eCRF page based on date of completion/discontinuation. Interruptions/washout periods between treatment periods (7 to 14 days) are not considered for duration of exposure. The mean duration of exposure in days will also be summarized.

Total exposure (in mL) will be based on the volume of residual product for AM dose of the first nebulization (RPL554 or Placebo dosing), or residual product of first and second nebulization (RPL554 or Placebo dosing), if applicable, and will also be summarized.

Drug accountability will also be summarized by treatment sequence for the RND analysis set. The number of vials dispensed will be compared to the number of unused vials returned, as measured on the Drug accountability eCRF page.

Document: Z:\RPL554\UYA25849\Biostatistics\Documentation\SAP\Verona RPL554-CO-204 SAP v1.0

Author: [name] Version Number: 1.0

Version Date: [18OCT2018]

Template No.: CS_TP_BS016 Revision 5 Reference: CS_WI_BS005

Effective Date: 01Apr2018

13.1. DERIVATIONS

- Duration of exposure (days) = date of last study medication administration date of first study medication administration number of washout period days between treatment periods (21 to 42 days) + 1.
- Total exposure (mL) = (number of vials dispensed x contents of each vial) residual product for AM dose of first (and second, if applicable) nebulization.
- Drug accountability (number of vials) = Number of vials dispensed number of unused vials returned.

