5.3 Preparation and Labelling

5.3.1 Nebulized RPL554 and Placebo

Vials of RPL554 and placebo will be packed as patient kits, one kit per period, each containing six vials, and labelled in compliance with GMP, released by a qualified person, where appropriate, and then shipped to the study center.

RPL554 and placebo are a unit dose 2.5 mL volume and will be prepared (poured into a nebulizer cup) by an unblinded individual who will not disclose the nature (appearance) of study treatment to the blinded Investigator and study center staff. The dose will be poured into a nebulizer cup, with is covered with tape to mask the color of the content.

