5.4.2.1 Nebulized RPL554 and Placebo

RPL554 and placebo will be administered by inhalation of an aerosol generated by a reusable PARI LC Sprint[®] jet nebulizer, with an exhalation filter, attached to a compressor (PARI TurboBOY[®] SX in the UK or a PARI VIOS Pro[®] in the US). Wherever possible, the same compressor unit should be used for each dose for a given a patient.

The dosing cup on each nebulizer will be obscured with opaque tape by study center personnel to visually blind the study medication.

The end time of nebulization (sputtering) will be considered Time 0 for the purposes of scheduling all post-dose study procedures. Nebulization time should be approximately 5 minutes and may not exceed 10 minutes. Patients must wear a protective gown on Day 3

Verona Pharma plc CONFIDENTIAL Page 25 of 66

during the dosing procedure to prevent contamination of the cannula for pharmacokinetic samples. Patients should be dosed in a well-ventilated environment, and away from other patients.

The following must be recorded in the eCRF:

- Compressor unit number
- Start and end times of nebulization (times will be rounded down to the nearest minute)
- The volume of residual product at the end of nebulization

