9.4.4 Extent of Exposure and Treatment Compliance

All administration of study treatment will be done at the clinic under supervision of the study staff; therefore, no formal analysis of compliance will be performed. The RPL554 exposure will be estimated based on residual volume in the nebulizer cup.

Verona Pharma plc CONFIDENTIAL Page 50 of 66

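### SAP 13.1 builds total exposure in mL from vials dispensed rather than vials used, and its residual term does not say which nebulizations it covers

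*SAP*

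**What the plan says.** Protocol 9.4.4 sets the aim: "The RPL554 exposure will be estimated based on residual volume in the nebulizer cup". Protocol 5.4.2.1 lists, among the items that must go in the eCRF, "The volume of residual product at the end of nebulization", without limiting this to morning or early doses. Supplies are packed as "one kit per period, each containing six vials" (Protocol 5.3.1), which matches the six doses per period in the Synopsis.

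SAP 13.1 turns this into a derivation with two terms:

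- **Volume supplied:** "number of vials dispensed x contents of each vial".
- **Subtraction:** "residual product for AM dose of first (and second, if applicable) nebulization".

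The body of SAP 13 words the subtraction slightly differently: the morning dose of the first nebulization, or "residual product of first and second nebulization (RPL554 or Placebo dosing), if applicable, and will also be summarized". The next bullet of SAP 13.1 derives drug accountability as vials dispensed less vials returned unused, but the mL formula does not use that count.

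On layout, SAP 13 is explicit for duration: "Exposure to study medication in days will be presented by treatment sequence for the RND analysis set". It gives the same grouping for drug accountability. For total mL it says only that the quantity will be summarized.

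**The concern.** Two parts of the formula can credit a patient with volume that was never nebulized.

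- The vial term treats a vial as exposure once it has been dispensed. The SAP itself expects some dispensed vials to come back unused, because it compares the two counts. The resulting error falls on patients who miss doses or stop within a period, whose exposure differs most from the nominal amount.
- The residual term names a first and perhaps a second nebulization, while up to six take place in each period. Any residual that is recorded but not subtracted is counted as nebulized.

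There is also a question of what the total represents. It covers RPL554 and placebo alike, and the SAP gives no RPL554-only version. If mL were added across treatments, it would not be the RPL554 exposure that the protocol says will be estimated.

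**Working it through.** **Inputs**

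- Fill volume 2.5 mL per vial; concentrations 0.6 and 2.4 mg/mL (Protocol 5.2.1).
- Six vials per kit, one kit per period (Protocol 5.3.1); six doses per period (Protocol Synopsis).
- Residual per nebulization, *r*: not given in the documents. I assume 0.25, 0.5 and 1.0 mL to show a range.
- Vials counted as dispensed: assumed to be the full kit of six.

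**Check against the plan's own figures.** 2.5 × 0.6 = 1.5 mg and 2.5 × 2.4 = 6.0 mg, so fill and concentration reproduce the two nominal doses.

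**Formulas, per treatment period**

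- SAP quantity = 6 × 2.5 − *k* × *r*, where *k* is the number of residuals subtracted.
- Volume actually nebulized = *d* × (2.5 − *r*), where *d* is the number of doses taken.

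**Vial term alone (*r* = 0)**

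| Doses taken | SAP (mL) | Nebulized (mL) | Excess |
|---|---|---|---|
| 6 | 15 | 15 | 0% |
| 4 | 15 | 10 | +50% |
| 2 | 15 | 5 | +200% |

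This part needs no assumption about residuals. Nor does settling the residual wording remove it: for four doses with *r* = 0.5 and all four residuals subtracted, the SAP gives 15 − 4 × 0.5 = 13 mL against 4 × 2.0 = 8 mL, an excess of 62.5%.

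**Residual term alone (completer, *d* = 6)**

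| Residuals subtracted | *r* = 0.25 (true 13.5 mL) | *r* = 0.5 (true 12.0 mL) | *r* = 1.0 (true 9.0 mL) |
|---|---|---|---|
| First only, *k* = 1 | 14.75 (+9.3%) | 14.5 (+20.8%) | 14.0 (+55.6%) |
| First two, *k* = 2 | 14.5 (+7.4%) | 14.0 (+16.7%) | 13.0 (+44.4%) |
| Three morning doses, *k* = 3 | 14.25 (+5.6%) | 13.5 (+12.5%) | 12.0 (+33.3%) |
| Morning and evening each day, *k* = 6 | 13.5 (0%) | 12.0 (0%) | 9.0 (0%) |

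**If mL were pooled across treatments (nominal, *r* = 0).** A patient who completes two periods shows 2 × 15 = 30 mL whatever the treatments were. The RPL554 received is 6 × 1.5 = 9 mg (1.5 mg and placebo), 6 × 6 = 36 mg (6 mg and placebo) or 9 + 36 = 45 mg (both active doses). The pooled mL is the same in all three cases.

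**The case against.** **The residual wording has an innocent reading.** Protocol 6.3.1.2, 6.3.2.2 and 6.3.3.2 call the evening administration the second dose of the day. If the SAP's first and second nebulizations are the morning and evening ones on each day, every residual is removed and a completer's figure is exact. This stands as a possible reading. It sits awkwardly with SAP 13.1, where the morning-dose qualifier precedes both terms, and neither SAP 13 nor 13.1 mentions each day or a sum over doses. The fair charge is an undefined term whose consequence ranges from nothing to large, not a demonstrated bias.

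**The vial term is harmless for most patients.** Six vials serve six doses, so dispensed equals used for anyone who takes them all. That is correct. Protocol 5.3.1 also describes packing, and does not say that the accountability page will record six vials for a patient who stops early. The 15 mL figures depend on that assumption.

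**Stronger readings the text does not support.** A reader might infer that mL will be shown by sequence, and hence that RPL554 exposure cannot be recovered. Grouping by sequence is stated for days and for accountability, on either side of the mL sentence, but not for mL itself; SAP 8 leaves layout to templates that are not among the documents. Summarized by treatment, mL multiplied by 0.6 or 2.4 mg/mL would give mg, subject to the two errors above. A reader might also infer that every patient's exposure is overstated. That fails for a completer under the morning-and-evening reading, or if residuals are zero.

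**The consequence is small.** Dosing is supervised in the clinic, recorded residuals should appear in the listings under SAP Appendix 1, and Day 3 plasma exposure is summarized by dose level (Protocol 9.4.6). All of this stands, and it limits the importance of the point without making the formula right.

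**Conclusion.** The vial term is wrong as written. It credits volume that was not nebulized whenever dispensed vials go unused, although the SAP defines the correct count in the next bullet. With no residual and the full kit counted as dispensed, the excess is 50% after four doses and 200% after two; it is zero for a patient who uses the whole kit.

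The residual term is undefined rather than shown to be biased. Across the readings and the assumed residuals of 0.25 to 1.0 mL, the excess for a completer runs from 0% to 56%.

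The grouping for mL is unstated. Only if treatments are pooled does the total fail to track RPL554 exposure.

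The impact is confined to the descriptive exposure summary. No efficacy or adverse-event analysis in the SAP uses mL. The point is worth correcting because the stated rule gives a wrong figure for patients who stop within a period and the correction is cheap.

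**What to change.** Replace the total exposure derivation in SAP 13.1 and align the paragraph in SAP 13:

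- For each patient and each treatment received, sum 2.5 mL minus the recorded residual over all administered nebulizations, morning and evening.
- Drop the reference to first and second nebulizations.
- State that the summary is by treatment received.
- Use vials dispensed less vials returned unused as a cross-check on the number of nebulizations, not as the source of the volume.
- Optionally, multiply by 0.6 or 2.4 mg/mL to report mg of RPL554. Protocol 9.4.4 does not require mg, so this is an addition rather than a correction.

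As an illustration, a completer with an assumed 0.5 mL residual would show 6 × 2.0 = 12.0 mL per period, which is 12.0 × 0.6 = 7.2 mg or 12.0 × 2.4 = 28.8 mg.

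The cost is one formula and one line on layout. The plan already has residual volumes and vial counts recorded in the eCRF, so no new data are needed.
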